### **3.6. Clinical Translational Science Institute (CTSI)**

The Clinical Translational Science Institute (CTSI) oversees DSMBs for clinical trials that require oversight, and assists in ensuring safe conduct of the study. For SOAP2, the CTSI works with the PI, IDSMB chair, and DCC to schedule meetings, develop agendas, and distribute materials.

### **3.7. Funding/Support**

Sources of support for this study include:

- National Heart, Lung, and Blood Institute (1R01HL120354-01A1 grant)
- The University of Pittsburgh's Building Interdisciplinary Research Careers in Women's Health (K12HD043441 grant)
- The Department of Obstetrics and Gynecology at the University of Pittsburgh's School of Medicine (additional funds provided, as needed)

## 4. Startup Requirements

### 4.1. Checklist

- NHLBI approval obtained (PI)
- IDSMB approval obtained (PI)
- HRPO/IRB approval obtained (PI)
- Clinical protocols modified for recruitment, screening and treatment of participants (DCC, PI)
- Data collection forms modified (DCC, PI)
- Electronic data collection, entry and management systems modified and tested (DCC, Clinical Team)
- Randomization procedures developed and tested (DCC, Clinical Team)
- Training materials modified (DCC)
- List of key personnel updated (PI)
- Completion of training by study personnel (Clinical Team, see below)
- Conflict of interest disclosures on file with the DCC (Leadership, Clinical Team, DCC, see below)

### 4.2. Training and Certification

The DCC provides training for clinical team members, to ensure quality and reliability of data and appropriate documentation of study progress and outcomes.

Topics include:

- Data collection forms
- Electronic data management system
- Randomization
- CPAP compliance tracking and incentive payments
- Adverse events and protocol deviations/violations
- Missed visits and missing forms
- Missing, out of range, or illogical data

Chart abstraction training entails abstracting two charts already abstracted by [name] and reviewing any discrepancies with [name].

At the conclusion of training, the DCC certifies clinical team members who demonstrate proficiency. Refresher training is scheduled, as needed, and recertification required, if appropriate.

Over the course of the study, the PI is expected to notify the DCC about new hires so that training and certification can be provided in a timely manner.

### 4.3. Conflict of Interest Disclosure

The PI and all co-investigators are required to disclose any ties to companies or individuals that could create conflicts (or dualities) of interest for the study. Disclosure statements are renewed annually and filed with the DCC.

## 5. Clinical Management

Clinical personnel recruit, screen and enroll participants, coordinate treatment, obtain specimens, and collect data at certain time points using forms developed or modified by the DCC for this study (see Table 2, below, and sections 5.1-5.6). Forms are included as an appendix to this MOP.

**Table 2: Data Collection Points, Related Forms and Delegation of Responsibility**

Form	Screening (EGA 6-19 6/7 wks)	Clinic Visit 1 (EGA 14-20 6/7 wks)	Home Visit	Clinic Visit 2 (EGA 28-31 6/7 wks)	Delivery/ Post Delivery	Other Time- point
Screening Questionnaire (SC)	RA					
Consent Documentation (CD)	RA					
Contact Information (CI) 	RA					
Initial Interview (II)	RA					
Sleep Log (SL)	[give]	[return]				
Sleep Questionnaire (SQ)		PARTICIP.		PARTICIP.		
Sleep Study (SS)		SBNC		SBNC		
Group Assignment (GRP)		COORD.				
Clinical Measurements (CM)		COORD.				
Maternal Bloods (MB)		COORD.		COORD.		
Uterine Artery Doppler (UA) 		COORD.		COORD.		
Home Visit (HV) 			SBNC	COORD.		
Delivery Specimens (DS)					OSPU	
IDSMB Outcomes (DO) 					COORD.	
Apnea Survey (AP) 					COORD.	
Chart Abstraction (CA) 					COORD. 	
Adverse Event (AE)	<----- COORD. (as needed) ----->					
Protocol Deviation (PD)	<----- COORD. (as needed) ----->					
Withdrawal (WD)	<----- COORD. (as needed) ----->					
Missed Visit (MV)	<----- COORD. (as needed) ----->					
Missing Form (MF)	<----- COORD. (as needed) ----->					
Other Data	Screening (EGA 6-19 6/7 wks)	Clinic Visit 1 (EGA 14-20 6/7 wks)	Home Visit	Clinic Visit 2 (EGA 28-31 6/7 wks)	Delivery/ Post Delivery	Other Time- point
NICOM 		[name]		[name]		
Maternal blood 		[name]		[name]		
Placenta 					[name]	
Placental biopsies 					PI	
Cord blood and plasma 					PI	

 Completed on paper only; not part of the electronic Data Management System

 Applies only to CPAP and Sleep Hygiene participants

 In consultation with PI

 Data collected and stored on NICOM machine by Study Coordinator then downloaded later by [name] in batches and sent to DCC in MS Excel format

 Processed later, in batches

 Stored for future studies

### 5.1. Recruitment and Screening

To identify potential participants for the SOAP2 study, the research assistant (RA) reviews prenatal medical records on the EPIC system and approaches women who meet basic inclusion criteria (i.e., aged 18 or older, 6-20 weeks pregnant, and obese) during their prenatal appointments to ascertain their

## Sleep-Disordered Breathing, Obesity and Pregnancy, Protocol 2 (SOAP2)

---

interest. This requires cooperation from the healthcare provider and his/her staff, so the PI reaches out to them to let them know about the study before their patients are approached.

Meanwhile, some women find out about the study on their own through Pitt+Me ([pittplusme.org](http://pittplusme.org)), a searchable database designed for individuals who are interested in getting involved in research; flyers or pamphlets posted throughout Magee-Womens Hospital (MWH); a slide displayed on the plasma screens in the lobby and near the elevators; or word of mouth. If they decide to contact the study team, they are prescreened in person or by phone.

The RA maintains a list of individuals who identify themselves or are approached and follows up with those who are interested during subsequent prenatal visits until a formal screening visit takes place. Repeated contact helps to ensure that those who ultimately enroll understand what is involved and are committed to completing the study.

During the formal screening visit, the RA confirms that the individual has not already been screened during this pregnancy or enrolled during a previous pregnancy long enough to complete the first sleep study, both of which are exclusion criteria. Next, a study ID is generated (see instructions, below) and a Screening (SC) form is completed, in person or by phone, to review the other exclusion criteria:

- A history of sleep apnea, insomnia, diabetes, heart disease, or lupus
- Prior use of a CPAP device
- Use of a breathing machine at night
- Currently pregnant with twins or higher order multiples (criterion added 6/1/15)
- Use of a sleeping aid more than once in the past month

### **Instructions: ID Generation**

1. Create a new record on the electronic data entry system (REDCap). A record ID (e.g., 81) will be automatically generated. Add 2000 to this record ID to generate the first part of the SOAP2 ID. If REDCap is not accessible, refer to the clinical data management tool developed by [name] to determine the next consecutive 4-digit number.
2. Add a dash ("-") followed by the participant's first and last initials (using capital letters) to create her ID (e.g., 2081-AH).

The SC is based on self-report; the RA does not refer to medical records or other sources to verify the accuracy of participant responses.

If the individual is found to be eligible, additional information is collected about sleep characterization and then details about the study are provided, including the timeline, the randomization process, potential risks and benefits, and the importance of compliance. Prior to seeking informed consent, which must be done in person, the RA reminds the individual that there is no obligation to participate or penalty for declining to participate, and that her care will not be compromised if she chooses not to participate or enrolls and subsequently leaves the study. Prospective participants must sign the consent form in order to proceed. The consent process is documented on the Consent Documentation form.

If informed consent is obtained, Contact Information (CI) is collected on a paper form and stored in a secure place at the study office; it is not entered into the electronic data entry system (REDCap). Next, an Initial Interview (II) is completed with questions about lifestyle, use of medications, prior pregnancies, and medical history, and self-reported estimated gestational age is confirmed by reviewing

the participant's medical record. Finally, the participant is given a 7-day Sleep Log (SL) along with instructions about how to record bedtimes, wake-up times, naps, and other information. Participants are expected to bring the completed SL when they come for Clinic Visit 1, which takes place 14-20 6/7 weeks EGA, so they need to receive the SL at least one week before then.

### **5.2. Clinic Visits: PSG, Maternal Bloods, Uterine Artery Doppler**

There are two overnight clinic visits, one scheduled during the second trimester (14-20 6/7 weeks EGA) and the other during the third trimester (28-31 6/7 EGA). Both take place at the Sleep and Behavioral Neuroscience Center (SBNC, formerly the Neuroscience Clinical and Translational Research Center) at Western Psychiatric Institute & Clinic (WPIC, part of UPMC). The instructions below are consistent with orders prescribed by the PI (see Appendix).

Prior to the each visit, the Study Coordinator reviews the participant's medical record to identify any medications that have been prescribed as well as diagnoses or symptoms that could affect her participation. Participants receive a reminder by phone, text, or email (based on personal preferences noted on the Contact Information form) of the coming visit and instructions to bring all medications with them. This is especially important for participants with hypertension. For the first visit, participants are also instructed to bring their completed Sleep Log (SL).

Each clinic visit begins in the evening when the participant arrives at the SBNC, usually 7-8PM.

Components include:

- Collection of the Sleep Log (SL) (Visit 1 only). The participant receives the SL from the Research Assistant during screening, completes it on paper, and returns it to the SBNC.
- Administration of a Sleep Questionnaire (SQ). The SQ covers general work and sleep patterns, sleep habits, snoring and sleep apnea. It is administered online. SBNC personnel complete the first part and the participant completes the rest. SBNC personnel are permitted to provide assistance, if requested by the participant, but should not rephrase questions. Prior to submitting, SBNC personnel are asked to review the form for completeness and encourage the participant to fill in any blanks.
- Initiation of the Sleep Study (SS) form. Weight is measured (this is not self-reported) and, after at least five minutes of rest, blood pressure is measured three times, with five minutes between measurements. Any readings >140/90 should be reported immediately to the medical contact.
- "Wire up." Small electrodes are placed on the participant's scalp, face, and legs so that technologists can monitor her air flow, body movements, heart rate, and oxygen saturation while she sleeps.
- Completion of the Sleep Study (SS) form. During the night, SBNC personnel review the participant's polysomnography (PSG) data to calculate an apnea-hypopnea index (AHI) estimate, using AASM 2012 rules. The AHI estimate at the first visit determines eligibility for randomization (see below). If a sleep study is not completed successfully – either because a participant refuses or there is a medical reason or technical problem – SBNC personnel should report this on the SSA and also notify the Study Coordinator. (Note: sleep studies are formally scored later on but these scores are recorded on the SBNC's "Harmony System," not REDCap.)
- Randomization (Visit 1 only). Participants with an AHI estimate 5-49 and who agree to be randomized are randomized by the Study Coordinator to CPAP or Sleep Hygiene for the treatment phase of the study (see "Randomization," below). For those randomized to CPAP, the assignment date, unit number, mask type, and other details are recorded on Group Assignment (GRP) form, and

use and care instructions, included in the case, are presented. For those randomized to Sleep Hygiene, general information is provided.

- Clinical measurements, maternal bloodwork, uterine artery ultrasound and NICOM data. After the PSG, participants are escorted by the Study Coordinator back to Magee. Clinical measurements (vitals, height, weight and waist, hip and neck circumference) are taken using the SOAP2 Tanita Protocol (see Appendix), along with three measures of blood pressure, and recorded on the Clinical Measurement (CM) form; fasting blood is drawn for cardiovascular risk profiles and documented on the Maternal Blood (MB) form; and a uterine artery (UA) Doppler is performed. Blood is processed and then stored for future batched testing. Non-invasive cardiac output monitoring (NICOM) is performed to measure cardiac function and output over a small interval of time (5-10 minutes).
- The Study Coordinator also takes this opportunity to review the Sleep Log, to see if there are any unusual responses, and the Sleep Questionnaire, to see if any responses are missing, asking the participant for clarification or additional information, as appropriate. In addition, during visit 2, the Study Coordinator asks CPAP participants whether all of the equipment is the same as what was originally issued and confirms that all components are still correctly labeled.

At the SBNC, eating is permitted until midnight. After midnight, only water is permitted until after fasting blood has been collected in the morning. Ideally, participants are asleep by 11PM but no specific good night time (GNT) has been established for the study.

An AHI estimate is calculated at both visits. At Visit 1, the AHI estimate determines group assignment (see 5.3, below). At Visit 2, participants who are in the Control Group and who have an AHI estimate of 5 or higher are given a referral to a sleep specialist (documented by the Study Coordinator as a "note to file").

Data are entered directly into REDCap, using the study laptop at the SBNC. If REDCap is not accessible, SBNC personnel enter data on a paper form and then give the paper form to the Study Coordinator the following morning so that the data can be entered into REDCap and/or visually verified, if it has already been entered by then. Visual verification is required for all forms completed on paper and is done by a different staff person or at least a day later, if done by the same staff person.

### **5.3. Group Assignment and Randomization**

A participant's AHI estimate from the first clinic visit determines whether she is randomized, assigned to the control group for observation only, or withdrawn from the study. Participants with an AHI estimate below 5 are assigned to the control group. They are not randomized. Participants with an AHI estimate of 50 or higher are referred to a sleep specialist and withdrawn from the study. They are not randomized. Participants with an AHI estimate 5-49 who agree to randomization are randomized by the Study Coordinator to CPAP or Sleep Hygiene, based on a system developed by the DCC (see below).

**Table 4: AHI Estimates, Study Assignment, and Instructions for Study Coordinator**

AHI Estimate	Assignment	Instructions for Study Coordinator
<5	Control	Tell participant that she does not have sleep apnea so she will not be in the treatment part of the study. Do not randomize.
5-49	CPAP or Sleep Hygiene	Tell participant that she is eligible for the treatment part of the study and ask if she agrees to be randomized. If she agrees, proceed with randomization (see Instructions, below). If she does not agree, do not randomize. Instead, let her know she will be withdrawn from the study.
≥50	Withdrawn	Tell participant that she has a degree of sleep apnea that requires attention and provide a referral to a sleep specialist. Do not randomize.

**Instructions: Randomization**

- 1) Select the next consecutively numbered Randomization Envelope, provided by the DCC. It is important not to skip any numbers.
- 2) Prior to opening the envelope, confirm that it is Visit 1, the participant is willing to be randomized, and her AHI estimate is 5-49.
- 3) Open the envelope to reveal her randomization assignment and then follow the prescribed script, documenting the process as directed on the Group Assignment (GRP) form, on REDCap.
- 4) File the randomization assignment sheet in the participant's research study folder, as source documentation.

**5.4. CPAP Equipment**

The Clinical Team is responsible for obtaining CPAP machines with cases and modems and labeling them with circuit numbers (C200-C236). The coordinator brings the units to the SBNC for distribution to eligible participants at Clinic Visit 1.

Each CPAP unit has a built-in hard drive that stores up to six months of data, a removable memory card that stores up to one year of data, and a modem configured to transmit data electronically. Data are transmitted to a secure, password-protected website (encoreanywhere.com) and are reviewed regularly by the PI to assess compliance and determine if the participant is eligible for incentive payments (see “Participant Compensation,” below). Data are accurate in real time only if modems are working properly. Otherwise, there may be a lag until data from the memory cards are transmitted.

**5.5. Home Visit and Weekly Calls/Texts**

CPAP participants are scheduled for a follow-up Home Visit (HV) by study personnel to try to address potential barriers to CPAP utilization. There is no defined window but, ideally, the visit occurs within two weeks of randomization. Additional visits may be scheduled, if needed. In addition to the home visit, the Research Assistant attempts to contact participants weekly by phone, text and/or email, depending on preferences recorded on the Contact Information (CI) form, to remind them to continue to use their CPAP machine.

Sleep Hygiene participants do not have a Home Visit but they receive monthly reminders, by phone, text and/or email, depending on preferences recorded on the Contact Information (CI) form.

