Miscarriages are documented on a Withdrawal (WD) form; all other APOs are documented during Chart Abstraction (CA) following delivery. For CPAP participants, APOs are also documented on the IDSMB Outcomes (DO) form. All other AEs are documented on Adverse Event (AE) forms. AE and APO data are pulled for weekly internal "Events" reports and are also included in bi-annual reports to the IDSMB. IDSMB reports are unmasked so that members can determine study-relatedness and consider whether the study needs to be modified or even terminated. Documentation and reporting requirements are summarized in the Diagram 1, below.

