This brings me to our request; we would like to change the RCT design (Aims 2 and 3) so that the arms are auto-CPAP vs an attention control. We would like to make this swap after we have randomized 45 individuals under the current design with a plan to randomize another 36 individuals after we switch to the unblinded and unmasked design. Those not randomized to CPAP would be informed of their SDB diagnosis, both verbally and also in a handout/letter. They would be informed that currently there are no treatment guidelines for SDB in pregnancy (a reiteration of wording from the consent form). We would offer some general sleep hygiene advice about getting regular and sufficient sleep and discuss how some women may get some alleviation from snoring by sleeping on their side, which some experts recommend for all pregnant women after 20 weeks gestation. We would conclude the letter by stating that if they have significant sleep disturbance or daytime sleepiness that they are concerned about that they should talk to their doctor about pursuing clinical testing. Contact information for a local sleep specialist would also be included.

Special Considerations:

A. Outcome Ascertainment

The main outcome measures of our study are outlined in Table 1 with a description of how unblinding/unmasking the control arm may impact ascertainment. In summary, we feel that the impact of unblinding/unmasking the participants, [name] and her research staff would be minimal as the individuals performing the ultrasound assessments and blood analyte measurements would remain blinded.

Chart abstraction would be carried out by unblinded study staff but the outcomes of interest for abstraction are clinically well defined and abstraction requires ascertainment of diagnoses (e.g., gestational diabetes, preeclampsia) along with supportive documentation (e.g. lab tests, blood pressures) so this would limit the potential for bias.

Table 1 Study Outcome Measures and Vascular Domain, Angiogenic Domain, Metabolic Domain		
Variable	Rationale	Considerations for unblinding/unmasking
Vascular Domain		

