Aim 2: To perform a randomized controlled trial of autotitrating- CPAP versus sham-CPAP in pregnancy to examine the impact of CPAP treatment during pregnancy on cardiovascular risk and describe adherence to treatment

Analysis modification plan: Our original sample size calculation for our trial called for a total of 68 subjects, 34 subjects in the active CPAP arm and 34 subjects in the sham CPAP arm. We are now proposing to increase our total N to 81. We would end recruitment in the active vs. sham trial when we have recruited a total of 45 participants. We would then start enrolling women to an active CPAP vs. sleep hygiene with the goal of recruiting 36 more participants' total (18 to active CPAP; 18 to sleep hygiene).

Aim 3: Explore interplay between SDB, CPAP and evidence of maternal vascular disease and chronic fetal hypoxia by evaluating the placental profile of obese women with and without SDB

Analysis modification for Aim 3 would follow the same construct outlined for aim 2, substituting the placental profile as the outcome of interest.

C. Analysis Plan

The analysis plan for the original aim would remain the same, **importantly this modification would have no effect on the detectable effect size or power calculation for Aim 1 as presented in our original application.**

The plan for the revised Aim 2 and 3 will follow in kind:

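### Open-label SOAP2 records non-obstetric adverse events only as needed, while CPAP women have about four to five times as many arm-specific contacts: a risk of unequal ascertainment

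*Protocol*

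**What the plan says.** **Masking and size.** The modification request in the SAP plans to "randomize another 36 individuals after we switch to the unblinded and unmasked design", "with the goal of recruiting 36 more participants' total (18 to active CPAP; 18 to sleep hygiene").

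**Contact by arm (SOAP2 manual, 5.5).** "CPAP participants are scheduled for a follow-up Home Visit (HV) by study personnel", ideally within two weeks of randomization and repeated if needed. In addition, "the Research Assistant attempts to contact participants weekly by phone, text and/or email". For the comparator, "Sleep Hygiene participants do not have a Home Visit but they receive monthly reminders". The stated purpose of the home visit is to deal with barriers to CPAP use, and that of the weekly contact is to prompt use. AEs are not mentioned.

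**How AEs are recorded.** Adverse pregnancy outcomes other than miscarriage come from chart abstraction, and miscarriage from the withdrawal form. For the rest, SOAP2 6.1 says: "All other AEs are documented on Adverse Event (AE) forms". Table 2 ties that form to no visit; its entry reads "COORD. (as needed"). The manual schedules no AE question in either arm.

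**Who uses the data.** AE data are part of the twice-yearly IDSMB reports. SOAP2 6.1 adds: "IDSMB reports are unmasked so that members can determine study-relatedness and consider whether the study needs to be modified or even terminated".

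**An internal conflict.** Table 2, footnote 2, marks the Home Visit form as applying to both randomized arms. Section 5.5 excludes Sleep Hygiene women from that visit.

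**The concern.** When an event enters the database only if staff hear of it, the recorded rate is the true rate multiplied by the chance of hearing. In SOAP2 that chance may differ by arm, because the opportunities to talk to staff differ and staff know the assignment.

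The difference came in with the new comparator. In SOAP1 (5.5), active and sham women shared the same home visit and weekly contact.

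The SAP's section on outcome ascertainment discusses the ultrasound and blood measures, chart abstraction and four obstetric or neonatal safety outcomes. It does not discuss other AEs. SOAP2 8.2 also says that no monitoring is done, whereas SOAP1 8.2 had annual visits and an audit of 10% of records. An AE that was never recorded is therefore less likely to be found later.

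At stake are the by-arm AE data that the IDSMB reads and the tolerability data for a larger trial. With 18 women per arm, a few unheard events would change the picture. No efficacy, power or alpha figure is affected.

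**Working it through.** The documents give no figure for AE ascertainment, so there is none to reproduce.

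**1. Contact counts.** Inputs: Visit 1 at 14–20 6/7 weeks, Visit 2 at 28–31 6/7 weeks (SOAP2, section 2) and the contact schedule in 5.5. Assumptions: delivery at 37–40 weeks, every weekly attempt counted, one home visit, one reminder per 4 weeks.

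- Visit 1 to Visit 2: shortest 28 − 20 6/7 = 7.1 weeks, longest 31 6/7 − 14 = 17.9 weeks. This gives 7–17 weekly contacts plus one home visit, against 1–4 reminders.
- Visit 1 to delivery: shortest 37 − 20 6/7 = 16.1 weeks, longest 40 − 14 = 26 weeks. CPAP: 16 + 1 = 17 to 26 + 1 = 27. Sleep Hygiene: 4 to 6.
- The ratio is 17/4 = 4.25 in the shortest case and 27/6 = 4.5 in the longest. Across delivery at 37, 39 and 40 weeks it runs from about 4.2 to 5.0.

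**2. What unequal detection would do.** With the same true risk p in both arms and detection probabilities dC (CPAP) and dS (Sleep Hygiene), the apparent risk ratio is p·dC / (p·dS) = dC/dS. The pairs below are assumed.

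| dC | dS | Apparent risk ratio |
|---|---|---|
| 0.9 | 0.9 | 1.00 |
| 0.9 | 0.7 | 1.29 |
| 0.9 | 0.5 | 1.80 |
| 0.8 | 0.4 | 2.00 |

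For example, with p = 0.40 and 18 per arm, 0.9 against 0.5 gives 18 × 0.40 × 0.9 = 6.5 against 18 × 0.40 × 0.5 = 3.6 women with a recorded AE.

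**3. A recall model, for illustration only.** Event times are uniform from Visit 1 to 40 weeks. An event is reported if a contact follows within the recall period. Visit 2 and delivery count in both arms, and reminders come every 30.4 days.

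| Recall | CPAP, all contacts succeed | Sleep Hygiene, all succeed | CPAP, half succeed | Sleep Hygiene, half succeed |
|---|---|---|---|---|
| 7 days | 100% | 28% | 55% | 19% |
| 14 days | 100% | 53% | 80% | 36% |
| 21 days | 100% | 76% | 91% | 51% |
| 28 days | 100% | 94% | – | – |

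Here "half succeed" applies to calls and reminders. The gap runs from large to small according to inputs the documents do not give. The model also assumes that every successful contact brings out the event.

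**4. What the common contacts alone would catch.** The mean Visit 1 is at (14 + 20.86)/2 = 17.43 weeks, so mean follow-up is (40 − 17.43) × 7 = 158 days. Visit 2 and delivery cover 2 × 7/158 = 9% of it at 7-day recall, 2 × 14/158 = 18% at 14 days and 2 × 21/158 = 27% at 21 days. A main table limited to these contacts would lose most minor events.

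**The case against.** A reader might infer that the AE data are in fact biased against CPAP. The documents do not support that, for these reasons.

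- **No elicitation is stated.** Nothing says AEs are asked about or noted at the home visit or weekly contact. Contact is only attempted and may be a text or email. This stands: existence and size are unknown. However, the manual schedules no AE enquiry anywhere, so unsolicited reports depend on opportunity, and a talk about barriers to CPAP use is likely to bring out symptoms.
- **Forms and scripts are not in view.** SOAP2 section 10 keeps them elsewhere, and the content of the Apnea Survey is not shown. The absence of a common AE question can be asserted only for the manual.
- **Shared routes exist.** The coordinator reviews every woman's record before each clinic visit (5.2), and chart abstraction covers maternal and postpartum complications (5.6). Hospitalizations would probably surface in both arms, so materially later discovery of serious events on Sleep Hygiene is not shown. One qualification: 5.6 requires review before entry for all CPAP charts, but for others only when certain items are flagged.
- **Many listed AEs do not fit an equal-rate premise.** Blood-draw, sleep-study and Doppler effects arise at procedures common to both arms. Mask and nasal complaints belong to CPAP, and an excess of them is a true effect.
- **The IDSMB's unmasked relatedness judgement is chiefly about pregnancy outcomes.** SOAP2 6.1 introduces unmasking in that context. Other AEs are nevertheless in the same reports.

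**Conclusion.** The point holds as a risk of differential ascertainment of non-obstetric AEs in SOAP2, probably towards more recorded events on CPAP. It rests on four features of the text: open assignment, an AE form with no scheduled time, about 4–5 arm-specific contacts on CPAP for each one on Sleep Hygiene, and unmasked IDSMB reports. The ratio assumes delivery at 37–40 weeks and that all planned contacts are made.

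The size of any distortion cannot be derived. The detection probabilities, recall periods and true risks in the working are assumptions. They span no distortion at equal detection to an apparent risk ratio of 2.00. A reader might take the recall model to show that most minor Sleep Hygiene events are missed and that CPAP events are not. It does not: at 28-day recall with full contact the gap is 94% against 100%, and if half of the calls succeed CPAP loses events too.

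The concern is mainly about minor and moderate events. It is worth correcting because the remedy is small and the pilot is meant to inform a larger trial.

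**What to change.** 1. In SOAP2 6.1 and Table 2, add the same short scripted AE question for every randomized woman at Visit 2 and at the delivery/post-delivery Apnea Survey.
2. Add a field to the AE form for how the event was learned: common visit, weekly contact, home visit, monthly reminder or chart.
3. Keep all AEs in the by-arm IDSMB table. Beside it, show a breakdown by source (common contact or chart, against arm-specific contact), with a between-arm comparison restricted to commonly ascertained events. The full table must remain, because CPAP complaints heard at weekly contacts are real harms that a restricted table would hide.
4. Reconcile Table 2, footnote 2, with 5.5 on which arms the Home Visit form covers. Also reconcile 6.1 with 5.6 on the IDSMB Outcomes form: 6.1 names only CPAP participants, 5.6 all randomized women.

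**Cost.** Manual wording, one question at two existing contacts and one database field. No extra visits or staff are needed, and the CPAP support schedule is untouched. The restricted comparison will catch few quickly forgotten minor events (about 9–27% at 7–21 day recall in the illustration, before chart-found events are added), so it supplements the full table and does not replace it.
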